### Materials and Methods

The scientific review committee and the committee for the protection of human participants of the local university (protocol number 1.376.881) approved this clinical investigation. It was registered in the clinical trials gov registry under the identification number NCT02956070. We performed this study using the protocol that the Consolidated Standards of Reporting Trials (CONSORT) statement established. Based on pre-established criteria, we selected 70 volunteers for this study. The study was performed from February 15, 2016, to July 12, 2016.

Two weeks before the bleaching procedures, each volunteer received a dental prophylaxis with pumice and water in a rubber cup and signed an informed consent form.

Study design: This was a randomized, triple-blinded, parallel-group clinical trial in which the volunteer, operator, and evaluator were blinded to the group assignment. A third researcher, not involved in the evaluation process, was responsible for the administration of the drugs. The study was carried out in the clinics of the School of Dentistry of Fluminense Federal University (Nova Friburgo, RJ, Brazil). Patients were recruited as they seek for treatment in the clinics of Dentistry of both Universities. No advertisement was made for participant recruitment. Patients were recruited in the order in which they reported for the screening session, thus forming a sample of convenience.

Inclusion and exclusion criteria: Volunteers included in this clinical trial were at least 18 years old, had good general and oral health, and did not report any type of TS. The volunteers were required to have 8 caries-free maxillary anterior teeth without restorations, be free of periodontal disease and review and sign the informed consent form. The central incisors had to be shade A1 or darker as judged by comparison with a value-oriented shade guide (VITA Classical, VITA Zahnfabrik). Despite the fact that the color shade A1 is one of the lightest colors measurable using VITA Classical, many volunteers with A1 shade teeth seek dental bleaching, as they are dissatisfied with the color of their teeth.

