Two calibrated investigators ([name]) independently performed the color evaluations with the shade guide. The 2 examiners, blinded to the allocation assignment, schedule the volunteers for bleaching and evaluated their teeth against the shade guide at baseline and 1 week after the procedure. The 2 examiners were required to have an agreement of at least 85% (Kappa statistic test) before beginning the study evaluation.

Volunteers with anterior restorations or dental prostheses, with anterior orthodontic apparatuses or with severe internal tooth discoloration (tetracycline stains, fluorosis, pulpless teeth) were not included in the study. In addition, pregnant and lactating women, participants with any other pathology that could cause sensitivity (such as gingival recession, dentinal exposure, visible cracks in teeth), those taking anti-inflammatory or analgesic drugs, those who smoked or volunteers who had undergone tooth-whitening procedures were excluded. Those who reported past or present health problems in the stomach, heart, kidneys or liver; those who reported the continuous use of anti-

inflammatory or analgesic drugs; those patients with diabetes, hypertension or the use of antihypertensive drugs; or patients who reported allergies to dexamethasone and lactose were also excluded from the study.

Sample size calculation: The primary outcome of this study was the absolute risk of TS. The absolute risk of TS (that is, the number of patients [percent] who reported pain at some point during dental bleaching) was reported to be approximately 90% for a similar 35% hydrogen peroxide bleaching product [20,21,36]. Thus, a minimum sample size of 70 participants was required to have a 90% chance of detecting, as significant at the 2-sided 5% level, a decrease in the primary outcome measure from 90% in the control group to 60% in the experimental group.

Random sequence generation and allocation concealment: The authors used blocked randomization (block sizes of 2 and 4) with an equal allocation ration, using a 3rd-party service (Sealed Envelope), which did not intervene in the study. Opaque and sealed envelopes containing the identification of the groups were prepared.

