Study intervention: We divided volunteers into the dexamethasone group, who received the anti-inflammatory (dexamethasone, capsule – 8 mg) and application of a placebo gel, and the control group, who received placebo capsules and the application of desensitizing gel containing 6% potassium nitrate and 0.10% fluoride sodium (Soothe, SDI, Victoria, Australia). All volunteers received the same bleaching treatment, which 4 experienced operators ([name]) performed. One week before the in-office bleaching session, volunteers received individual pots containing 6 capsules in total, with the dexamethasone (Handled by Bem Viver laboratory Ltda), or placebo, in identical capsules depending on their allocation group, which contained the same components of the dexamethasone drug except for the active ingredient (Table 1).

The control group received placebo capsules and the application of desensitizing gel containing 6% potassium nitrate and 0.10% fluoride sodium, and the dexamethasone group received the anti-inflammatory (dexamethasone, capsule - 8mg) and application of a placebo gel. Volunteers were treated in 2 clinical sessions with an interval of 7 days (one week) between them. The protocol for use of the product was as follows: The volunteers in the experimental group received 6 capsules of dexamethasone 8 mg each, which was administered orally, initially 2 days before the 1st bleaching query (8mg, 9 AM, 2 days before the bleaching session; 8mg, 9 AM, 1 day before the bleaching session; 8mg, 9 AM, on the day of the bleaching session) [40]. This same scheme was performed for the 2nd bleaching session, which was 7 days after the 1st. The operators instructed the volunteers to increase adherence to the protocol, and the researches made telephone calls and sent cell phone text messages to remind the volunteers of every capsule to be taken.

Before the dental bleaching, gingival tissue was isolated from teeth using a light-cured resin (Gingival Barrier, SDI), and each tooth was light-cured for 10 seconds using a light curing unit with 1200 mW/cm2 light intensity (Radii-cal, SDI). After the placement of a lip retractor (OptraGate – Ivoclar Vivadent), the operator used the 37.5% hydrogen peroxide gel (polaoffice+, SDI) in three 8-

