minute applications for both groups in accordance with the manufacturer's directions. The bleaching agent was refreshed every 8 minutes during the 24-minute application period. At the end of each session, a single researcher responsible for the blinding [name] delivered a single syringe to the operator, which would contain desensitizing gel if the patient was in the control group, or placebo gel containing only carbopol (no active ingredient) if the patient was in the dexamethasone group. The gel was applied with a brush on the labial surface of the whitened teeth for 2 to 3 minutes as the manufacturer (Soothe SDI Dental Limited) directed. Two bleaching sessions were performed 1 week apart.

TS evaluation: TS was evaluated during bleaching and up to 1 hour, 24 hours and 48 hours postbleaching. The volunteer was asked to indicate the numeric value of the degree of sensitivity for each of the periods above, using a 5-point numeric rating scale (NRS) in which 0= none, 1= mild, 2= moderate, 3= considerable and 4= severe [2,4,5,7,23].

In addition, the volunteers were also instructed to record the pain intensity using the visual analogic scale (VAS) [3,6-9]. This scale is a 100-milimeter horizontal line with scores of 0 and 100 at their ends, in which 0 = no sensitivity and 100 = severe sensitivity. The volunteer had to mark with a vertical line across the horizontal line of the scale the intensity of the TS. Then, the distance in millimeters from the zero ends was measured with the aid of a millimeter ruler.

The data from each bleaching session were evaluated separately and were merged. For this purpose, the worst score or numeric value obtained in both bleaching sessions was considered for statistical purposes and the determination of the overall risk and intensity of TS.

If the volunteer scored 0 (no sensitivity) in all time assessments from both bleaching sessions, this volunteer was considered to be insensitive to the bleaching protocol. In all other circumstances, the volunteers were considered to have sensitivity stemming from the bleaching procedure. This dichotomization allowed us to calculate the absolute risk of TS, which represented the percentage of volunteers who reported TS at least once during treatment. We also calculated the overall TS intensity.

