PRODUCT	INGREDIENTS
Pola Office + SDI*	• 37.5% hydrogen peroxide
	
 
potassium nitrate
 

Soothe SDI*	• potassium nitrate 6.0%
	• fluoride ions 0.10%
	• water 89.60%
	• thickener 4.20%
	• sodium benzoate 0.10%
Dexamethasone capsules**	
 
dexamethasone base 8mg
 

•	• starch 50%
	
 
lactose monohydrate 35%
 

	
 
dibasic calcium phosphate 14%
 

	• magnesium stearate 1%
Placebo capsules**	• starch 50%
	
 
lactose monohydrate 35%
 

	
 
dibasic calcium phosphate 14%
 

	• magnesium stearate 1%
Placebo gel**	• carbopol

\* SDI, Victoria, Australia

\*\* Handled by Bem Viver laboratory Ltda, registration number 09047030/0001-28, located at [name]. Batch of the product: 189155.

# TABLE 2

Participants who exp	erienced too	th sensitivity d	uring the bleaching regi	men in the control group	
and dexamethasone g	group*				
TREATMENT	TOOTH SENSITIVITY (N°. OF PARTICIPANTS)		ABSOLUTE RISK	RISK RATIO (95% CONFIDENCE	
	Yes	No		INTERVAL)	
Control	33	2	0.94	0.24 (0.05 1.26)	
Dexamethasone	28	7	0.80	0.24 (0.05 – 1.26)	
* Fischer's exact test	(p=0.075).				

TABLE 3

Medians and interquartile (1 and 3 interquartile) ranges of the tooth sensitivity at different assessment points using the numeric rating scale (NRS).

ACCECCMENT		First Session		Second Session			
ASSESSMENT TIMES	Control	Dexamethason e	Compariso n group	Control	Dexamethason e	Comparison group	
During bleaching	$0(0-1)^{A}$	0 (0-1) A	NS †	0 (0-1) A	0 (0-1) A	NS	
Up to 1h after bleaching	0 (0-1) A	0 (0-1) A	NS	0 (0-1) A	1 (0-1) A	NS	
Up to 24h after bleaching	0 (0-1) A	0 (0-1) A	NS	0 (0-2) A	0 (0-1) A	NS	
Up to 48h after bleaching	0 (0-0) B	0 (0-0) B	NS	0 (0-0) B	0 (0-0) B	NS	

\* Within each column, significant differences are represented by different uppercase letters.

† NS: No significant difference between groups.

TABLE 4

 $Means \ (standard \ deviations) \ of \ the \ tooth \ sensitivity \ intensity \ at \ the \ different \ assessment \ points \ using \ visual \ analog \ scales.*$ 

A COLECCI MENTE	First Session			Second Session		
ASSESSMENT TIMES	Control	Dexamethasone	Compariso n group	Control	Dexamethason e	Comparison group

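### Only the capsules are stated to match; the placebo gel is specified as carbopol alone, so masking to the gel is not assured, mainly for the four operators

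*Combined protocol and SAP*

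**What the plan says.** Under Study design (Materials and Methods) the trial is called a "triple-blinded, parallel-group clinical trial in which the volunteer, operator, and evaluator were blinded to the group assignment". Under Study intervention, the dexamethasone arm takes active capsules and gets a placebo gel, and the control arm takes placebo capsules and gets the desensitizing gel. That is a double-dummy design.

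For the capsules the matching is explicit. They were supplied "in identical capsules depending on their allocation group, which contained the same components of the dexamethasone drug except for the active ingredient", and Table 1 shows the same four excipients at the same percentages in both.

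For the gels there is no such statement. The operator's syringe held desensitizing gel for a control patient, or "placebo gel containing only carbopol (no active ingredient) if the patient was in the dexamethasone group". Table 1 also lists carbopol as the placebo gel's single ingredient. The control gel has five listed components, among them a thickener whose type is not named ("thickener 4.20" per cent).

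The safeguard described for the gel is that one researcher, responsible for blinding, hands the operator a single syringe at the end of each session. The operator then brushes the gel on for 2 to 3 minutes. The document does not mention matching of the gels' appearance, consistency or taste, the labelling of the syringes, or any check of blinding.

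**The concern.** A double-dummy design masks the arm only if both dummies resemble their active counterparts. Here one pair is matched on paper and the other is specified with a different composition. Handing over a single syringe conceals the assignment code, but it does not conceal how the gel looks or spreads once it is in use.

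The primary outcome is the absolute risk of tooth sensitivity. It is rated by the volunteer alone, and under TS evaluation one non-zero score at any time in either session makes that volunteer a case. An endpoint of this kind can respond to small shifts in self-report. If an operator recognised the gel, remarks or manner could reach the volunteer before most of the ratings are made.

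**Working it through.** **1. The two dummies side by side (Study intervention and Table 1)**

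| | Active | Placebo | Stated to match? |
|---|---|---|---|
| Capsule | dexamethasone plus starch 50%, lactose 35%, dibasic calcium phosphate 14%, magnesium stearate 1% | same four excipients, same percentages | Yes |
| Gel | potassium nitrate 6.0%, fluoride 0.10%, water 89.60%, thickener 4.20%, sodium benzoate 0.10% | carbopol | No |

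The control gel's components sum to 6.0 + 0.10 + 89.60 + 4.20 + 0.10 = 100.0%, so its listing is complete. The placebo gel's listing gives one ingredient and no vehicle.

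**2. How often an operator meets each gel**

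Inputs: 70 volunteers, 35 per arm (Table 2), 4 operators, 2 sessions. Assumption: volunteers are shared evenly among operators, with arms balanced within operator.

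- Volunteers per operator: 70 / 4 = 17.5.
- Gel applications per operator: 17.5 × 2 = 35.
- Of each gel: 35 / 2 = 17.5.

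On that assumption an operator would have many chances to compare the two gels. A volunteer has two applications of the same gel and nothing to compare it with.

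**3. Ratings that follow a gel**

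Inputs: four rating times per session (during bleaching, then up to 1, 24 and 48 hours after), two sessions, gel applied at the end of each session. I assume the 1-hour rating was recorded after the gel.

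- Rating times per scale: 4 × 2 = 8.
- After a gel in the same session: 3 × 2 = 6 of 8.
- After any gel: 8 − 1 = 7 of 8. The extra one is the session 2 rating during bleaching, which follows only the gel of a week earlier.

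**4. How little movement would matter**

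This shows how sensitive the endpoint is. It does not estimate bias. The Table 2 counts, 33/35 control and 28/35 dexamethasone, give a two-sided Fisher p of 0.151; the printed 0.075 is the one-sided value. With control held at 33/35, 27/35 on dexamethasone gives a two-sided p of 0.084 and 26/35 gives 0.045. In the other direction, 29/35 gives 0.259. Two volunteers classified differently would be enough to cross the 5% level.

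**The case against.** The strongest reply is that a difference in composition need not be perceptible. The control gel's thickener is unnamed, so the documents cannot show that the two gelling agents differ. The placebo was brushed on as a gel, so it must have had a vehicle that Table 1 leaves out. Table 1 also gives only two ingredients for the bleaching product, so its listings are not all full formulas. Counting five components against one therefore overstates the physical contrast. Nothing shows that plain, identical syringes were not used, and a separate researcher's hand-over is a real, if partial, safeguard. All of this stands. It limits the point to masking that is not assured. It does not remove the point, because matching was documented for one dummy while the other was specified with a different make-up.

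The reply is also right about volunteers: each meets one gel, and people with previous whitening were excluded.

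A reader might go further in three ways that the documents do not support.

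- **That blinding failed.** No evidence of unmasking is given.
- **That operators could predict later assignments, given** "blocked randomization (block sizes of 2 and 4"**.** No route is described. The examiners scheduled volunteers, allocation used a third-party service and opaque sealed envelopes, and capsules were given out a week before the first session.
- **That the session 1 rating during bleaching is a check of the primary comparison free of unblinding.** It is already in Tables 3 and 4, where the mean VAS is 8.09 against 7.51, a difference of 0.58. The later VAS differences, control minus dexamethasone, run from 0.77 to 7.57, and the contrast invites a story about unblinding. But at that first rating no control volunteer had received desensitizing gel, so it compares the capsules only. Later differences could reflect drug, gel or chance.

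**Conclusion.** The concern holds in a limited form. The triple-blind claim is supported for the capsules. It is not assured for the gel, chiefly for the operators and, mostly indirectly, for the volunteers who supply the primary outcome. The exposure is six of eight rating times on the same-session count and seven of eight on the wider count. The amount and direction of any bias cannot be derived from the documents. The shade evaluators are not implicated: they are described as masked and assess colour a week after each session.

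This rests on taking the stated composition at face value and on the document's silence about appearance, consistency and syringes. If the sponsor can show that gels and syringes were indistinguishable, the point reduces to a gap in reporting.

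**What to change.** **For the plan or a future trial.** Specify the placebo gel as the control gel's vehicle: water, the same type and amount of thickener, and sodium benzoate, without potassium nitrate and fluoride. Check it against the control gel for appearance and consistency before use. Have the researcher responsible for blinding load both gels into identical unlabelled syringes.

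**For the completed trial.** State whether the gels and syringes were matched. If they were not, limit the triple-blind statement to the capsules and the shade evaluators, and say that masking of operator and volunteer to the gel was not assured.

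**Cost.** A laboratory already compounds the placebo gel and one researcher already hands over the syringes, so the added work is a different formula, a comparison of the gels and a transfer step. The type of thickener would first have to be identified, since Table 1 does not name it. For the completed trial the cost is a possibly weaker blinding claim.

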## Statistical analysis

We performed the analysis after the intention-to-treat protocol, and we involved all participants who were randomly assigned [21]. In cases of missing data, the last observation was carried forward. The statistician was masked to the study groups. The absolute risk of TS and its intensity were evaluated by using Fischer's exact test. ( $\alpha = 0.05$ ). The authors calculated the relative risk as the confidence interval for the effect size.

Comparison of the TS intensity (NRS data) of the 2 groups at the 2 different assessment points were performed by using the Mann-Whitney U test, and comparisons between times within each group were performed using the Friedman test. The comparisons of the TS intensity obtained with the VAS scale were evaluated by using a 2-way repeated measures ANOVA and Tukey's test.

Color changes between groups ( $\Delta$ SGU between base line versus 1 week after the 2nd bleaching session) were compared by using a t test, and the shade changes were evaluated by using Student's t test. In all statistical tests, the significance level was 0.05. We performed all analyses by using the software SPSS for windows version 20.0 (IBM).

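### The overall worst 0–4 sensitivity score is derived but never tested as an ordered score, and the Results draw a general no-effect conclusion from an any-versus-none primary outcome

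*Combined protocol and SAP*

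**What the plan says.** In Materials and Methods, the sample size paragraph states that "The primary outcome of this study was the absolute risk of TS". It assumes 90% in the control group and 60% in the experimental group at a two-sided 5% level, and concludes that "a minimum sample size of 70 participants was required to have a 90% chance of detecting" this difference.

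The TS evaluation paragraph defines the ratings as "0= none, 1= mild, 2= moderate, 3= considerable and 4= severe", taken at four periods in each of two sessions, so eight per volunteer. For the overall risk and the overall intensity, "the worst score or numeric value obtained in both bleaching sessions was considered for statistical purposes". A volunteer with 0 at all eight ratings is insensitive and everyone else is sensitive; "This dichotomization allowed us to calculate the absolute risk of TS". The same paragraph adds that overall intensity was calculated.

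The Statistical analysis section begins "The absolute risk of TS and its intensity were evaluated" and names Fisher's exact test for both. Mann-Whitney is named for the NRS data by assessment point, and repeated-measures ANOVA for the VAS.

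Table 2 reports 33 of 35 control and 28 of 35 dexamethasone volunteers as sensitive (p = 0.075). Tables 3 and 4 compare the arms rating by rating. No table or sentence compares the arms on the overall worst score. From Table 2 the Results text concludes that the drug regimen did nothing to reduce sensitivity.

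**The concern.** A single mild rating out of eight counts the same as repeated severe pain, and a change from severe to mild counts as no change. With 90% of controls expected above the cut, only volunteers moved to zero at all eight ratings can contribute to a difference.

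The worst score could show a reduction in severity, and the plan already derives it. Fisher's test treats its five levels as unordered, and the result is not reported in any case. The rating-by-rating Mann-Whitney tests do not fill the gap, because they give eight separate comparisons and no overall one.

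What is at stake is the breadth of the conclusion. A non-significant any/none comparison can support a statement about the proportion with any sensitivity. It cannot support a statement that the drug has no effect on sensitivity in general.

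**Working it through.** **Inputs.** From the sample size paragraph: 90% versus 60%, two-sided 5%, 70 volunteers. The allocation text gives "blocked randomization (block sizes of 2 and 4) with an equal allocation ration", so 35 per arm. The documents do not give the distribution of the worst score, so the split of sensitive controls over scores 1–4 is an assumption and is varied.

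**The plan's own figure.** The usual pooled formula gives

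n per arm = [1.960·√(2·0.75·0.25) + 1.282·√(0.9·0.1 + 0.6·0.4)]² / 0.30² = (1.200 + 0.736)² / 0.09 ≈ 41.7, so 42 per arm or 84 in total.

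The stated 70 for 90% power is not reproduced. The comparison below therefore uses power computed at 35 per arm and not the nominal 90%.

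**Power on the any/none cut.** Exact enumeration over two binomials (n = 35 each) gives 78.5% for two-sided Fisher and 85.2% for Pearson chi-square. The difference of 6.7 points is Fisher's conservatism near the ceiling; its type I error at 90% versus 90% is about 1.3%.

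**Power on the worst 0–4 score.** The planned effect corresponds to an odds ratio of (0.9/0.1)/(0.6/0.4) = 9/1.5 = 6. Control P(0) is 0.10 and dexamethasone P(0) is 0.40. Each assumed split gives the control distribution, and the dexamethasone distribution follows from the odds ratios at each cut. For the 60/25/10/5 split with a common odds ratio of 6, scores 0 to 4 have 10/54/22.5/9/4.5% in controls and 40/51.4/6.0/1.8/0.8% on dexamethasone. Simulated power (%) of the tie-corrected Mann-Whitney test:

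| Split of sensitive controls over 1/2/3/4 | Odds ratio 6 at all cuts | Odds ratios 6,3,3,3 | Equal severity among the sensitive | Only mild moves to none |
|---|---|---|---|---|
| 80/15/4/1 | 92.8 | 86.0 | 71.6 | 52 |
| 60/25/10/5 | 96.1 | 86.2 | 65.4 | 31 |
| 45/30/15/10 | 97.4 | 85.8 | 62.7 | 21 |
| 30/40/20/10 | 97.9 | 84.0 | 61.5 | not possible |
| 25/25/25/25 | 98.3 | 83.3 | 60.8 | not possible |

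The last column needs at least 30% of all controls at mild. The bottom two rows have 0.9 × 30% = 27% and 0.9 × 25% = 22.5%. Mann-Whitney type I error was 4.8–5.1%.

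**Reading the table.**
- Common odds ratio of 6: the gain over chi-square on the same cut runs from 92.8 − 85.2 = 7.6 to 98.3 − 85.2 = 13.1 points. This is the part due to the ordinal scale.
- Odds ratios 6,3,3,3: 83–86%, above Fisher and about level with chi-square.
- Last two columns: below Fisher's 78.5%.
- The first column shrinks further if mild dominates more strongly. With 80% of all controls peaking at mild, power is about 90%; with 85%, about 88%.

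**The case against.** The strongest reply is that nothing is defined wrongly. Zero is the scale's own anchor for no sensitivity, any-versus-none is a clear clinical question, and the 90% comes from cited studies of a similar product. Intensity is also examined: NRS by Mann-Whitney and VAS by ANOVA, both reported as showing no difference. All of this stands, and it is why the primary outcome should not be replaced. What remains is that no ordered test of the overall score is named or reported.

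A reader might infer several stronger claims that the documents do not support.

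- *The ordinal scale gains 14–20 points.* That is the distance from Fisher, and 6.7 of those points are Fisher's conservatism. Chi-square is also arguably closer to what was run: for 33/2 versus 28/7 two-sided Fisher gives 0.151, while the reported 0.075 equals the one-sided value and is near chi-square (0.074).
- *The VAS already shows a severity effect.* The Table 4 means sum to 77.25 mm in controls and 44.19 mm on dexamethasone, a ratio of 0.57 against a risk ratio of 28/33 = 0.85. With Table 4's SDs and an assumed within-person correlation of 0.2 to 0.8, the approximate 95% interval runs from 0.36–0.92 to 0.27–1.23 and includes 0.85 throughout. A sum of VAS means also does not determine the distribution of the worst NRS score. On the NRS, medians and quartiles are identical between arms at 6 of 8 ratings.
- *The zero medians in Table 3 show that the cut is misleading.* They coexist with 94% and 80% sensitive because sensitivity is taken as the maximum over eight ratings. An ordinal test of the worst score keeps that maximum.
- *The ordinal test should decide the conclusion.* Choosing it after a non-significant primary result would be data-driven selection.

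**Conclusion.** The point holds as a modest improvement in analysis and interpretation, not as an error in the primary outcome. The overall worst score is derived, assigned a test that ignores its order, and left without a reported comparison, while the Results draw a conclusion wider than the any/none test can carry.

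The ordinal scale would add about 8–13 points of power over chi-square on the cut. This rests on 35 per arm, the planned 90% versus 60%, a common odds ratio of 6 at every cut, and the assumed severity splits. The documents support neither the common odds ratio nor any particular split. If the drug changes only whether pain occurs, the ordinal test is weaker than Fisher: 61–72% with equal severity among the sensitive, and about 21–52% if only mild scores move to none. Replacing the primary would therefore be a trade-off that also changes the question asked. Because the trial is complete, its planned power cannot change either.

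**What to change.** 1. Keep the any/none absolute risk as the primary outcome and report it as now.
2. For overall intensity, replace Fisher's test by one ordinal analysis of the worst 0–4 score: either a tie-corrected Mann-Whitney test with the probability of superiority, or a proportional-odds model with a common odds ratio. Give a 95% CI and tabulate the five score levels by arm. Label it post hoc.
3. Word the primary conclusion as *no significant difference in the proportion with any sensitivity*, in place of the general no-effect statement, whatever the ordinal analysis shows.

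The cost is one further analysis on data already held, with no new volunteers, visits or ratings. The downsides are that it adds a post hoc result, that a common odds ratio is less familiar than a percentage, and that the test is less sensitive than the any/none comparison if the drug affects only the presence of pain.
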